8.9.3 Tumour Lysis Syndrome

Tumour lysis syndrome is generally not considered to be DLT. The syndrome should be reported in 24 hours to Sponsor if Grade 3 or Grade 4.

When there is a suspicion of a tumour lysis syndrome (plasma phosphate level >4.5 mg/dL (1.5 millimole per litre (mmol/L), plasma potassium level >6.0 mmol/L, and plasma albumin corrected calcium <7.0 mg/dL (1.75 mmol/L) or ionized calcium <1.12 (0.3 mmol/L), treatment with intravenous fluids and phosphate binders should be initiated. Rasburicase, a recombinant urate oxidase enzyme, should be considered if serum creatinine levels increase 2.0–2.9 fold from the baseline. If the increase is higher, rasburicase treatment should be started immediately. When subjects are treated with rasburicase, the blood samples used for the measurement of the uric acid level must be placed on ice to prevent ex vivo breakdown of the uric acid by rasburicase and thus obtaining a spuriously low level.

The administration of FP-1305 can be continued when a tumour lysis syndrome occurs, especially when cancer is responding to the treatment. However, prophylactic medication (allopurinol 300 to 800 mg/day in divided doses) may be considered, and proper intravenous hydration should be ensured.

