4.1 Dose Limiting Toxicity

DLT evaluable subjects include:

- Part I: All subjects
- Part II: The first three (or six if there is one DLT in the first three) subjects in the following cohorts
 - Q3W cohorts at dose levels that have not previously been tested in Part I
 - Q2W cohorts at each new dose level for the Q2W schema
 - Q1W cohorts at each new dose level for the Q1W schema
- Part III: DLT not applicable

DLT assessment period in Part II is shorter than in Part I, justified by the safety and tolerability data collected during the trial and enabling prompt dose escalation as a part of the 3+3 design of Part II.

- Part I: 63 days (9 weeks) following the first dose of FP-1305
- Part II: 28 days (4 weeks) following the first dose of FP-1305

A DLT is defined as a drug related AE \geq Grade 3 according to NCI-CTCAE version 5.0 occurring during the DLT assessment period and related to FP-1305. The following are exceptions to the rule:

- Grade 3 infusion reactions that resolve within 8 hours from the onset of the reaction are not defined as a DLT
- Grade 3 nausea/vomiting or diarrhea for less than 72 hours with adequate antiemetic and other supportive care are not defined as a DLT
- For thrombocytopenia, haemorrhage is required to qualify grade 3 toxicity as DLT; Grade 4 thrombocytopenia is DLT regardless of haemorrhage
- For neutropenia DLT is as follows,
 - Any neutropenic fever
 - Grade 3 neutropenia persisting $>$ 5 days or Grade 4 neutropenia
- For toxicity judged to be consistent with an acute infusion-related reaction or cytokine release syndrome, DLT will be defined as follows (Sehn 2012):
 - Grade 4 drug-related AE or
 - Grade 3 drug-related AE that cannot be resolved by infusion rate reduction or interruption, or supportive care.
- An AE which, in the opinion of the Investigator, is attributed to a study subject's underlying disease will not be considered a DLT.

In addition, the following are considered DLTs (occurring during the DLT assessment period and related to FP-1305):

- Grade ≥ 2 ALT or AST increase accompanied with bilirubin elevation $>2x$ ULN if baseline value was normal; $>2 \times$ baseline if baseline value was abnormal
- Dose delay of the 2nd cycle due to drug-related toxicity of >14 days

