A serious adverse event (SAE) may be considered a DLT according to this section. The severity of the AEs will be codified according to the NCI-CTCAE version 5.0. If the subject has an event that meets the DLT criteria otherwise, but it is not considered to be drug related, then the reason needs to be clearly documented. The sites are requested to report the DLTs via electronic case report form (eCRF) immediately within 24 h an event meets the DLT criteria. In case the eCRF cannot be updated with the DLT (e.g. technical issue), sites are to email to Medical Monitor immediately within 24 h stating a suspected DLT has occurred. The SAE reporting according to [Section 11.4](#) is required in any case to all events that meet the SAE criteria.

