To ensure the safety of the study subjects, the first three subjects at and above the 30 mg/kg dose level will be enrolled stepwise after each has cleared their 28 day DLT observation period. The detailed rules for enrolling the first three subjects on a dose level are described below (4.3.2). If any of the first three subjects dosed at the 30 mg/kg dose level has a DMC verified DLT (see [Section 4.1](#) for DLT definition) within 28 days from the first IMP administration, an additional three subjects will be enrolled on the 30 mg/kg dose level. If a maximum of one of the six subjects experiences a DLT at 30 mg/kg dose level, up to ten subjects will be included in the 30 mg/kg dose level after which the trial can proceed to the next dose level. If at least two of the first three subjects or two of the six subjects experience a DMC verified DLT at the 30 mg/kg dose level, then the MTD has been reached, enrolment to the 30 mg/kg dose level will be placed on hold and dose escalation is terminated. The MTD is defined as the highest dose level, in which the first six subjects were treated with a maximum of one subject experiencing a DLT. Subjects on treatment who have not experienced DLT at that dose level may continue receiving the treatment and the DMC will decide regarding the treatment continuation and possible dose level de-escalation for these particular and DLT experienced subjects. The doses 45 and 100 mg/kg Q3W have the same 3 + 3 dosing rules as described for 30 mg/kg, and if at least two of the first three subjects or two of the six subjects has a DLT, then the MTD has been reached, enrolment to the dose level will be placed on hold, and dose escalation is terminated. If MTD is achieved at the dose level of 30mg/kg Q3W, a reserve de-escalation dose level of 20 mg/kg Q3W may be investigated with the same 3+3 design approach.

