4.3.2 Dosing Rules (30 - 100 mg/kg) (Q3W, Part II)

Sentinel dosing will be applied for 30-100mg/kg dosing. The second subject on a particular dose level can receive the first dose only after the first subject has been followed up for 28 days (additional precaution compared to traditional 3+3 model) after the first dose, and has not demonstrated any DLT. The third subject may receive the first dose after the second subject has been followed up for 28 days after the first dose and and neither of the subjects have demonstrated any DLTs. DLT evaluable subject will have at least one dose of IMP and have at least 28 days of follow-up after IMP infusion. If these criteria are not met, the subject will be replaced. Once three evaluable subjects have received at least one dose and have been followed up at for 28 days with no DLTs, all remaining subjects on the dose level may be enrolled without any hold. If any of the first three subjects cannot be followed for the full 28-day DLT observation period for reasons other than DLT, the subject may be replaced in order to obtain the required tolerability information of 28 days from the first IMP infusion, before the remaining subjects on the dose level may be enrolled. The replaced subject will, however, count towards the cohort of 10 subjects. The same rules will apply for the other dose levels.

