Based on the MoA properties, FP-1305 is predicted to induce immune cell activation. This activation might lead to immune-related adverse reactions. Thus, special attention should be given to fever, diarrhoea, colitis, transaminase or total bilirubin elevations, signs and symptoms of nephritis, renal dysfunction, endocrinopathies, hyperglycaemia, changes in the thyroid function, or rash. Study subjects may present with fatigue, headache, mental status changes, abdominal pain, unusual bowel habits, and hypotension, or nonspecific symptoms which may resemble symptoms caused by e.g. brain metastasis or the underlying disease. However, since FP-1305 is suspected to only induce direct tumour effects, the likelihood of irAEs is expected to be low.

Tumour lysis syndrome: Tumour lysis syndrome is an oncologic emergency that develops most often in patients with non-Hodgkin's lymphoma or acute leukaemia, its frequency is increasing among patients who have tumours that used to be only rarely associated with this complication. The onset may vary, but after Rituximab (EU)/Rituxan (US) therapy it occurs after 12-24 hours of the first infusion. It occurs when tumour cells release their contents into the bloodstream, either spontaneously or in response to therapy, leading to the characteristic findings of hyperuricemia, hyperkalaemia, hyperphosphatemia, and hypocalcaemia. These electrolyte and metabolic disturbances can progress to clinical toxic effects, including renal insufficiency, cardiac arrhythmias, seizures, and death due to multiorgan failure. Hyperphosphatemia with calcium phosphate deposition and/or the precipitation of uric acid in the renal tubules can also cause acute kidney injury.

With the emergence of new effective and targeted anticancer drugs or new combinations of drugs, tumour lysis syndrome has also been observed in patients with cancers that were previously rarely associated with this complication. At least one case of tumour lysis syndrome has been observed with anti-CSF1R therapy. It is possible that also FP-1305 can cause tumour lysis syndrome because it can direct cytotoxic T-cells to kill tumour cells. FP-1305 may also impair macrophage phagocytosis function, a MoA that may predispose to tumour lysis syndrome if a massive anti-tumour effect is achieved.

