8.9.1 Infusion Reactions

In case of an infusion reaction, the following documentation should be recorded

- 1) Pre-infusion assessment (i.e., the drugs administered, doses, number of previous infusions of the agent, and infusion rates)
- 2) Initial symptoms and course of progression

- 3) Time when the infusion was initiated and time when the infusion reaction began
- 4) Intervention, timing, and subject response
- 5) Time of symptom resolution

Infusion reactions are generally not considered to be DLT, but this judgement should be conducted after each case. Severe (Grade 3 or 4) reactions should be reported within 24 hours to the Sponsor.

Grade 1 infusion reaction (Mild reaction; no infusion interruption or intervention necessary)

Monitor the subject closely or treatment according to the local practise. Consider prophylactic medication (e.g., paracetamol a.k.a. acetaminophen and diphenhydramine) for next administration.

Grade 2 infusion reaction (Moderate reaction leading to infusion interruption but responsive to symptomatic treatment): Interrupt the infusion but maintain vascular access with normal saline. Paracetamol (a.k.a. acetaminophen) and diphenhydramine (or other antihistamine according to local practises) usage is recommended or treatment according to the local practise. However, diphenhydramine (50 mg) and ranitidine (50 mg diluted in 5% dextrose to 20 mL) given together for anaphylaxis are superior to diphenhydramine given alone. Vital sign assessment should be periodically repeated until the subject is stable. Once the symptoms are totally resolved, the infusion may be restarted at maximum 50% of the previous infusion rate. If the symptoms do not recur during 30 minutes of infusion of this slower rate, the infusion rate may be increased to the normal rate. If symptoms recur, the infusion must be stopped, and the amount infused should be reported. Prophylactic medication for the next administration is highly recommended and the infusion rate should be adjusted (see [Section 8.2.1](#) and [Section 8.2.2](#)).

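### Section 8.9.3 says tumour lysis syndrome is generally not a DLT and gives no criterion, while Section 4.1, which the Part II 3+3 rule cites, counts a related Grade 3 or higher case within 28 days

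*Protocol*

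**What the plan says.** **Definition.** Protocol Section 4.1 makes a drug-related adverse event of Grade 3 or higher a DLT when it is "occurring during the DLT assessment period and related to FP-1305. The following are exceptions to the rule". The listed exceptions cover infusion reactions, nausea, vomiting and diarrhoea, thrombocytopenia, neutropenia, cytokine release syndrome, and events the investigator attributes to the underlying disease. Tumour lysis syndrome is not among them. The Part II window is 28 days. DLT-evaluable subjects are the first three in each new exposure cohort, or six if one of the three has a DLT.

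**Toxicity management.** Section 8.9.3 says "Tumour lysis syndrome is generally not considered to be DLT". Its next sentence requires Grade 3 and 4 cases to reach the sponsor within 24 hours. It gives no criterion for when a case is a DLT, does not refer to Section 4.1, and allows dosing to continue through the syndrome, especially in a responding patient.

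**Decision rules.** Section 4.3.1 refers to Section 4.1 for the DLT definition. A level goes forward under this condition: "If a maximum of one of the six subjects experiences a DLT at 30 mg/kg dose level, up to ten subjects will be included". Escalation ends when this count is met or exceeded: "two of the first three subjects or two of the six subjects experience a DMC verified DLT at the 30 mg/kg dose level"; the same rule applies at 45 and 100 mg/kg. Under Section 4.3.2 the second subject is dosed only once the first has been followed for 28 days "after the first dose, and has not demonstrated any DLT", and the third only if neither earlier subject has had one.

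**Plausibility.** Section 8.8 says: "It is possible that also FP-1305 can cause tumour lysis syndrome because it can direct cytotoxic T-cells to kill tumour cells".

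**The concern.** A site that sees a related Grade 3 or higher case within 28 days has two instructions. Section 4.1 makes it a DLT. Section 8.9.3 says it generally is not, and supplies no test for the exceptions. Sites file DLTs "immediately within 24 h an event meets the DLT criteria", so a site guided by 8.9.3 might not file a case that 4.1 counts.

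The infusion-reaction text shows what is missing. Section 8.9.1 says: "Infusion reactions are generally not considered to be DLT, but this judgement should be conducted after each case". That statement has a case-by-case clause, and Section 4.1 has matching infusion-reaction entries. Tumour lysis has neither.

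Two decisions depend on the count: release of the next sentinel subject, and the stop at two DLTs in six. DLT occurrence over 28 days is also how the Part II primary outcome judges the tolerability of new doses (Section 3.10).

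**Working it through.** The documents state no operating characteristic for the Part II 3+3 rule, so there is no figure of the plan's to reproduce. The check is a comparison of texts, followed by an illustration under assumed rates.

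**Step 1: which cases are in conflict.**

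| Case | Section 4.1 | Section 8.9.3 |
|---|---|---|
| Unrelated, or attributed to the underlying disease | Not a DLT | Generally not a DLT |
| Related, Grade 3 or higher, within 28 days | DLT | Generally not a DLT, no criterion |

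Only the second row conflicts.

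**Step 2: effect on the rules.**
- One such case plus one other DLT in a different subject among six: 2/6 under 4.1, so escalation ends; 1/6 if 8.9.3 is applied as an exclusion, so the level continues.
- One such case and no other DLT: the level continues either way, because 1/6 is allowed.
- One such case in subject 1 or 2: the next sentinel subject is barred under 4.1 but not under that reading of 8.9.3.

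**Step 3: chance that a level passes.** Let t be the rate per subject of related Grade 3 or higher tumour lysis within 28 days, and p the rate of other DLTs, independent of it. Both are assumptions; 20% is the Part I target DLT rate (Section 4).
- DLT rate under 4.1: q = 1 − (1 − t)(1 − p). Under full exclusion: p.
- The level passes with no DLT in three, or with one in three and none in the next three: pass(x) = (1 − x)³ + 3x(1 − x)⁵.

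Worked case, t = 1% and p = 10%: q = 1 − 0.99 × 0.90 = 0.109.
- Under 4.1: 0.891³ + 3 × 0.109 × 0.891⁵ = 0.7073 + 0.1836 = 0.891.
- Under full exclusion: 0.9³ + 3 × 0.1 × 0.9⁵ = 0.7290 + 0.1771 = 0.906.

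| t | p = 5% | p = 10% | p = 20% |
|---|---|---|---|
| 0.5% | 96.9% v 97.3% | 89.9% v 90.6% | 70.0% v 70.9% |
| 1% | 96.3% v 97.3% | 89.1% v 90.6% | 69.1% v 70.9% |
| 2% | 95.2% v 97.3% | 87.5% v 90.6% | 67.4% v 70.9% |
| 5% | 91.0% v 97.3% | 82.4% v 90.6% | 62.2% v 70.9% |

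Each cell is 4.1 v full exclusion. From unrounded values, the gap at t = 1% is 1.0, 1.5 and 1.7 percentage points. Across the table it runs from 0.5 to 8.7.

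**Step 4: given exactly one case in the first three subjects, t = 1%.** Under 4.1 the level passes only if the other two subjects have no other DLT and the next three have no DLT of any kind: (1 − p)²(1 − q)³. Under full exclusion the case carries no information, so the chance is pass(p).
- p = 5%: 0.95² × 0.9405³ = 75% v 97%.
- p = 10%: 0.90² × 0.891³ = 57% v 91%.
- p = 20%: 0.80² × 0.792³ = 32% v 71%.

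**Step 5: sentinel gate.** The chance of a tumour lysis case in subject 1 or 2 is 1 − (1 − t)², which is 2.0% at t = 1% and 9.8% at t = 5%.

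Section 4.3.2 does not say how dosing resumes after a sentinel DLT. Steps 3 and 4 assume enrolment goes on to six under Section 4.3.1, and apply to the Q3W levels.

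**The case against.** The strongest reply is that one operative definition already exists. Section 4.3.1 cites Section 4.1, and the filing instruction sits inside 4.1. Section 8.9 is about managing toxicity, so generally can be read as an expectation, not a competing rule. A missed filing would not hide the case either: Grade 3 and 4 tumour lysis goes to the sponsor within 24 hours (8.9.3), SAE reporting applies in any event (4.1), and the DMC verifies DLTs (4.3.1) and reviews toxicity and other relevant data (17.2). Most of this stands and limits the consequence. It does not remove the inconsistency. DMC verification supplies no tumour lysis criterion, and 8.9.3 does not say that its 24-hour report prompts a DLT review.

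The calculation is also a worst case. It reads generally as never, applies that at every site and lets no safeguard act. The 5% tumour lysis rate has no basis in the documents. Both criticisms stand.

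Scope is narrow. The Part II SAP (Section 4) says a 30 mg/kg cohort was already recruited. Protocol Section 4.3 includes 45 and 100 mg/kg only as possibilities. The Q2W and Q1W rules are in an Addendum not provided here.

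Three stronger readings are tempting, and the documents do not support them:
- *The protocol excludes tumour lysis from DLTs.* The word generally is not a flat exclusion.
- *The Part I result is in doubt.* The Part I SAP reports no DLT in 30 subjects, and neither document reports a tumour lysis case, so nothing indicates that one was left uncounted.
- *The Step 4 contrasts measure the expected effect.* They apply only once a case has occurred; the Step 3 differences are the unconditional ones.

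**Conclusion.** The point holds as an internal inconsistency in a decision rule: wrong as written, low severity. For a related Grade 3 or higher tumour lysis case within 28 days, Section 4.1 and Section 8.9.3 point in different directions, and 8.9.3 offers no way to reconcile them. The conflict is live only in the first three to six subjects of a new Part II exposure cohort still to be dosed. One case could decide the sentinel gate; the 2-of-6 stop changes only if another DLT also occurs.

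The unconditional effect is small if the syndrome is rare: 1.0 to 1.7 percentage points in the chance of passing a level at an assumed 1% rate, for other-DLT rates of 5% to 20%. This rests on assumed rates, independence, 8.9.3 applied as a full exclusion, no safeguard acting, and enrolment continuing to six. The reason to act is that the rule should be settled before a case occurs.

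**What to change.** Replace the first sentence of Section 8.9.3 with: *Whether a case of tumour lysis syndrome is a DLT is determined by Section 4.1.*

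If the sponsor intends an exclusion, which the allowance to continue dosing in 8.9.3 suggests it may, add a defined tumour lysis exception to the Section 4.1 list, with grade and resolution limits, and have 8.9.3 refer to it. Either route leaves one definition for sites and the DMC.

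The first route costs one sentence in the protocol. Its downside is that, without an exception, a case reflecting anti-tumour effect could slow or stop escalation. The second avoids that for cases within the stated limits, but the sponsor must set them in advance.

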⁴ Predose assessment at screening, Cycles 1, 2, 4, 6, and every second cycle thereafter; and Follow-up; postdose assessment at Cycles 1 and 4; ECG must be performed also always if clinically indicated

⁵ Pregnancy test for women of child-bearing potential only. Screening and Follow-up visit: test in serum, Predose assessments: test in serum or urine.

⁶ Cycles 1, 2, 3 and 4 only; Post IMP administration timepoints in Cycles 1 and 2: 0 h after infusion and flushing the line, 1 h (+/- 5 mins), 5 h (+/- 30 mins), D2 (+/- 4 h), D3 (+/- 4 h), D4 (+/- 4 h), D5 (+/- 8 h), and D8 (+/- 24 h)

⁷ Cycles 1, 2, 4, 6, and every second cycle thereafter, or if clinically indicated, and Follow-up

⁸ Predose assessments, local and research laboratory blood samples are permitted to be taken up to three days before the Day 1 of each cycle. The only exception is vital signs which should be taken on the day of IMP administration

⁹ Complete blood cell counts: white blood cells, neutrophils, lymphocytes, platelets, haemoglobin

¹⁰ Comprehensive metabolic panel: glucose, calcium, sodium, potassium, chloride, creatinine, ALT, ALP, AST, CK, total bilirubin, albumin.

¹¹ Screening, predose at every cycle; postdose at Cycle 1 D5 (+/- 8 h), Cycles 2 and 3 D8 (+/- 24 h), and Follow-up

¹² Endocrine panel: cortisol, lipase and pancreas-specific amylase, thyroid stimulating hormone, PTH, free thyroxine (T4), free triiodothyronine (T3), troponin on all cycles

¹³ Screening test may be immunochemical. If positive, nucleic acid test should be performed on Cycles 1, 2, 4 and 6. If negative at screening no additional tests should be performed

¹⁴ At selected sites and cohorts only. Predose assessment in Cycles 1 and 2. Post IMP administration timepoints in Cycle 1: D2 (+/- 4 h), D8 (+/- 24 h), and D15 (+/- 24 h)

¹⁵ Collected at sites that do not collect 'Blood sample for RO and PBMC' (see footnote 14 above). Predose assessment in Cycles 1 and 2. Post IMP administration timepoints in Cycle 1: D2 (+/- 4 h), D8 (+/- 24 h), and D15 (+/- 24 h)

¹⁶ Analysed from the plasma fraction of the blood sample collected for PBMC isolation or blood sample for RO and PBMC during Cycle 1 predose, D2 (+/- 4 h), D8 (+/- 24 h) and D15 (+/- 24 h) and Cycle 2 predose. Collected as an independent sample in Cycle 2 D2 (+/- 4 h), D8 (+/- 24 h), D15 (+/- 24 h), and Cycle 3 predose. See Central Laboratory Services manual for further details.

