 - Blood sample for PBMC isolation (only in Cycle 1) D5 (+/- 4 h)
- AE assessment. NOTE: AE assessments should be conducted each time the subject is visiting the hospital. Photographs to document visible Aes should be considered.

8.4.5 Samples Collected and Parameters Analysed during and after IMP Administration in Part II

During or after the IMP infusion, parameters for safety and blood samples are collected as follows (see also [Table 2](#) and the Laboratory Manual):

- Vital signs (blood pressure, heart rate, body temperature and respiratory rate)
 - Cycles 1-3: 20 minutes after the start of the infusion, 40 minutes after the start of the infusion and at 1 h after the start of the infusion or at the end of the infusion (immediately after flushing the line), whichever occurs later. For the subsequent infusions vital signs are to be measured only before and after IMP infusion.
 - in Cycle 1 at 5 hours (+/- 2 hours) after IMP infusion completion
- PK sampling (only in Cycles 1 and 2)
 - 0 h after all IMP has been administered, 1 h (+/- 5 mins), 5 h (+/- 30 mins), D2 (+/- 4 h), D3 (+/- 4 h) D4 (+/- 4 h), D5 (+/- 8 h), and D8 (+/- 24 h)
- Tumour biopsy (only in Cycle 2 and if any new lesions)
 - Cycle 2 biopsy should be obtained within 10 days after the IMP administration. See the Laboratory Manual for sample procurement and handling procedures.
 - Biopsy from new lesions is recommended if assessed feasible by the investigator considering the location of the lesions and condition of the subject.
- ECG (only in Cycles 1 and 4)
 - 0 h after the infusion and PK sampling
- Blood samples
 - CBC on D5 (+/- 8 h) (only in Cycle 1)
 - CMP on D5 (+/- 8 h) (only in Cycle 1)
 - CMP on D8 (+/- 24h) (only in Cycles 2 and 3)
- Research blood samples
 - At selected sites and cohorts only: Blood sample for RO and PBMC isolation (only in Cycle 1) D2 (+/- 4 h), D8 (+/- 24 h) and D15 (+/- 24 h)
 - Blood sample for PBMC isolation when 'Blood sample for RO and PBMC' is not collected (only in Cycle 1) D2 (+/- 4 h), D8 (+/- 24 h) and D15 (+/- 24 h)
 - sCLEVER-1 RO sample (only in Cycles 1 and 2) D2 (+/- 4 h), D8 (+/- 24 h) and D15 (+/- 24 h)
 - Flow cytometry (TBNK cells, CD127 FOXP3 Assay and PD-1 T-Helper Assay) (only on Cycles 1 and 2) D2 (+/- 4 h), D8 (+/- 24 h) and D15 (+/- 24 h)
 - Cytokine and chemokine panel (only on Cycles 1 and 2) D8 (+/-24 h) and D15 (+/- 24 h)

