8.9 Management of Toxicities

All AEs should be graded according to [Section 11.3.1](#) and proper action taken based on the clinical findings and grading.

In the following, when a limit for a laboratory parameter in plasma is indicated and the local practice is to have the test in serum, the equivalent value should be considered, and vice versa.

FP-1305 should be withheld for any of the following adverse event at least possibly related to FP-1305:

- 1) Grade 2 pneumonitis (see [Section 8.9.2.1](#))
- 2) Grade 2 or 3 colitis (see [Section 8.9.2.2](#))
- 3) Grade 2 nephritis (see [Section 8.9.2.3](#))
- 4) Grade 2 liver enzyme elevations (see [Section 8.9.2.4](#))
- 5) Grade 2 or 3 endocrinopathy (see [Section 8.9.2.5](#))
- 6) Grade 2 fibrosis due to liver injury (see [Section 8.9.4](#))
- 7) Any other severe or Grade 3 treatment-related adverse reaction
- 8) Prolonged (> 2 weeks) Grade 2 or intolerable Grade 2 toxicity

FP-1305 must be permanently discontinued for any of the following adverse event at least possibly related to FP-1305:

- 1) Any life-threatening adverse reaction (excluding endocrinopathies controlled with hormone replacement therapy and/or immunosuppressants)
- 2) Grade 3 or 4 infusion reaction (see [Section 8.9.1](#))
- 3) Grade 3 or 4 pneumonitis or Grade 2 recurring pneumonitis (see treatment in [Section 8.9.2.1](#))
- 4) Grade 4 colitis (see [Section 8.9.2.2](#))
- 5) Grade 3 or 4 nephritis (see [Section 8.9.2.3](#))
- 6) Grade 3 or 4 hepatic failure (see [Section 8.9.2.4](#))
- 7) Grade 4 endocrinopathy (see [Section 8.9.2.5](#))
- 8) Grade 3 or 4 fibrosis due to liver injury (see [Section 8.9.4](#))
- 9) Inability to reduce the corticosteroid dose to 10 mg or less of prednisone or equivalent per day within 6 weeks from the initiation of the continuous corticosteroid
- 10) Persistent Grade 2 or 3 adverse reactions (excluding endocrinopathies controlled with hormone replacement therapy and/or immunosuppressants) that do not recover to Grade 0-1 within 6 weeks after the last dosing of FP-1305 and that are considered clinically significant
- 11) Any haematological or non-haematological Grade 3 treatment-related adverse reaction that recurs

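### Protocol 8.9.3 lets FP-1305 continue in tumour lysis syndrome of any grade, while 8.9 requires stopping for related life-threatening or recurrent Grade 3 reactions; its suspicion criteria also need phosphate, which no scheduled panel measures

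*Protocol*

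**What the plan says.** **Action.** Protocol 8.9.3 (Tumour Lysis Syndrome) says of severe cases: "The syndrome should be reported in 24 hours to Sponsor if Grade 3 or Grade 4". It then says: "The administration of FP-1305 can be continued when a tumour lysis syndrome occurs, especially when cancer is responding to the treatment". Neither sentence limits continuation by grade, recovery or relatedness.

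Protocol 8.9 (Management of Toxicities) has two lists, both restricted to events at least possibly related to the drug.
- The withholding list opens: "FP-1305 should be withheld for any of the following adverse event at least possibly related to FP-1305". Its catch-all item is "Any other severe or Grade 3 treatment-related adverse reaction".
- The permanent-discontinuation list is worded as an obligation. It opens with "Any life-threatening adverse reaction (excluding endocrinopathies controlled with hormone replacement therapy and/or immunosuppressants" and closes with any related Grade 3 reaction that recurs.

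Protocol 10.4 makes the occurrence of toxicities defined in 8.9 a reason for which dosing and participation must stop.

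**Suspicion criteria.** Section 8.9.3 sets limits for phosphate (above 4.5 mg/dL), potassium (above 6.0 mmol/L) and albumin-corrected calcium (below 7.0 mg/dL) or ionised calcium, joined by an 'and'. The chemistry panel in the schedules is: "Comprehensive metabolic panel: glucose, calcium, sodium, potassium, chloride, creatinine, ALT, ALP, AST, CK, total bilirubin, albumin".

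**The concern.** Section 8.8 treats tumour lysis syndrome as an emergency and gives reasons why FP-1305 could cause or predispose to it, so a case judged related is foreseeable. An investigator facing a related life-threatening case finds an obligation to stop in one place and permission to continue in another, with no order of precedence.

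The first stake is the safety of the subject concerned. The second is consistency: two sites could follow different texts and both be compliant. The Part II SAP (14.1) tabulates adverse events leading to discontinuation by disease group. In cohorts of ten, each subject handled differently moves such a proportion by 1/10, or 10 percentage points.

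The suspicion criteria raise a smaller point. Criteria that start treatment should be assessable from the scheduled data, or the protocol should say that they rely on tests ordered on clinical suspicion. It does neither.

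**Working it through.** No sample size, power or error rate is involved; the check sets the texts side by side.

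**Step 1: can tumour lysis syndrome fall under the 8.9 lists?** Yes. The lists cover related events, Section 8.8 says FP-1305 may cause the syndrome, and 8.9.3 itself anticipates Grades 3 and 4. Table 5 (Section 11.3.1) describes Grade 4 by life-threatening consequences, and the 8.9.2 subsections pair the two terms. A Grade 4 case therefore meets the life-threatening item.

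**Step 2: is the syndrome exempted?** No. The life-threatening item states one exemption, for controlled endocrinopathies. The two lists cross-refer to 8.9.1, 8.9.2.1 to 8.9.2.5 and 8.9.4, but never to 8.9.3.

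**Step 3: compare by grade and relatedness.**

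| Tumour lysis syndrome | Section 8.9 | Section 8.9.3 | Result |
|---|---|---|---|
| Not related, any grade | Lists do not apply | May continue | No conflict |
| Related Grade 1, or Grade 2 that is neither prolonged, intolerable nor persistent | No item applies | May continue | No conflict |
| Related Grade 2, prolonged (over 2 weeks) or intolerable | Should withhold | May continue | Partial |
| Related, first Grade 3 | Should withhold | May continue | Partial: withholding is temporary |
| Related, recurrent Grade 3 | Must stop permanently | May continue | Direct |
| Related, life-threatening | Must stop permanently | May continue | Direct |

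A related Grade 2 or 3 event that is clinically significant and has not recovered to Grade 0-1 within 6 weeks of the last dose also falls under the permanent-discontinuation list.

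**Step 4: can the suspicion criteria be met from scheduled tests?**

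| Limit in 8.9.3 | Scheduled in Tables 1 to 3? |
|---|---|
| Potassium | Yes, metabolic panel |
| Albumin-corrected calcium | Yes, from calcium and albumin in the metabolic panel |
| Phosphate | No |

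The metabolic panel has the same analytes in Parts I, II and III (Table 1 footnote 10, Table 2 footnote 10, Table 3 footnote 13). The endocrine panels cover cortisol, lipase, amylase, thyroid hormones and PTH, plus troponin in Parts II and III. The other scheduled blood tests (counts, serology, LDH, LDL, CRP, tumour markers, research samples) do not add phosphate. With the limits joined by 'and', two of three can be read from scheduled data, so the full set cannot be met.

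Creatinine, which 8.9.3 uses for its rasburicase guidance, is scheduled. Uric acid, for which 8.9.3 gives sample-handling instructions, is not, but it is not one of the three limits.

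**The case against.** **A specific section may override a general list.** On this view 8.9.3 is the rule for tumour lysis syndrome and the 8.9 lists govern the rest. Section 8.9 also opens by asking for action according to clinical findings and grade, and 10.4 points to 8.9 as a whole, which contains 8.9.3. This may be the intent, but the protocol does not say so. The life-threatening item carries an explicit exemption and could have named the syndrome; it does not.

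**Continuation is permissive and withholding is temporary.** This stands for a first Grade 3 event: dosing can be withheld and later resumed without breaching either text. It does not help where 8.9 requires permanent discontinuation.

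**Detection does not rest on the scheduled panel alone.** This also stands in part. Section 8.2.1 allows longer hospitalisation for subjects thought to be at risk of the syndrome and requires 24 h of monitoring for Part I escalation subjects and the first three Part II subjects at new doses or frequencies. Adverse events are assessed at each hospital visit. Potassium and calcium are scheduled and could prompt further tests. None of these provisions specifies a phosphate test.

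**A stronger reading about timing is tempting.** The first scheduled post-dose chemistry is Cycle 1 Day 5 (Sections 8.4.4 to 8.4.6), and a reader might infer that it falls too late for the onset given in 8.8. That sentence reads: "The onset may vary, but after Rituximab (EU)/Rituxan (US) therapy it occurs after 12-24 hours of the first infusion". It describes another drug and begins by saying that onset varies; the protocol gives no onset time for FP-1305. Screening and pre-dose chemistry also exist. A timing mismatch is therefore an analogy, not an internal contradiction, and it gives no ground for asking for earlier blood draws.

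**Conclusion.** The contradiction is real and limited. It is direct in two situations, related life-threatening and related recurrent Grade 3 tumour lysis syndrome, and partial for a first related Grade 3 event. It does not reach unrelated cases, or lower grades outside the prolonged, intolerable or persistent Grade 2 rules. The documents give no expected number of cases, so its frequency cannot be estimated.

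The phosphate gap is also real: one of three joint limits has no scheduled measurement in any part. This assumes that 'and' is meant literally. If any single limit were enough, scheduled potassium or calcium could raise suspicion without phosphate.

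A reader might go further and infer that cases will be missed, or that the safety data could not support a statement that none occurred. The documents do not show the first, since clinical assessment and unscheduled tests remain available. They neither make nor plan the second claim, and Section 11.5 does not list the syndrome as an event of special interest. No view is taken here on which dosing rule is clinically right.

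**What to change.** 1. Reconcile 8.9.3 with the withholding and permanent-discontinuation lists in 8.9. State which text prevails for tumour lysis syndrome by grade, recurrence and relatedness, and add the missing cross-references between 8.9 and 8.9.3.
2. Align 10.4 with the result, so that its pointer to 8.9 has one meaning for this syndrome.
3. Reconcile the 8.9.3 suspicion criteria with the scheduled laboratory panels, and make explicit whether all limits must be met together and whether the criteria are to be read from scheduled tests or from tests ordered on suspicion.

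The sponsor, medical monitor and DMC decide the clinical content of each item. The cost is protocol amendment wording and its approval. Sample size, endpoints and planned analyses are unaffected. Any laboratory cost depends on how item 3 is resolved.
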